NCT05257837

**Follow-up Gun Study:
Can Safety Videos Mitigate Interest in Guns in Children?**

Statistical Analysis Plan

Uploaded 4/5/2023

Statistical Analysis Plan

Data Collection

Data will be collected in two ways. First, some data are entered directly into Qualtrics surveys by parents/guardians and participants in the home and in the lab. In the home, parental consent, child assent, and questionnaire data (i.e., gender, age, trait aggressiveness, age-inappropriate movie consumption, interest in guns, whether participants had taken a firearm safety course or watched a firearm safety video, and whether participants had a firearm at home) will be collected directly online via Qualtrics. In the laboratory, participants will also provide questionnaire data (i.e., attitudes towards guns, whether they have fired a gun before, safety video evaluation, movie evaluation) on iPads via Qualtrics. Second, participants' reporting and handling of the handguns (i.e., whether the child found the gun, told an adult about the gun, touched a gun, time spent handling a gun, total trigger pulls, trigger pulls while pointing the gun at the partner/self) will be recorded via video using a hidden camera. The videos will be coded by trained research assistants who are blind to experimental conditions and study hypotheses.

Data Cleaning

Data cleaning will be done in Excel, SAS, and R. Once the data have been cleaned, the variables will each be examined via summary statistics. Internal reliability of the survey batteries will be assessed via Cronbach's alpha and McDonald's omega. If necessary, variables will be transformed to conform to the assumptions of the statistical tests. Potential outliers will be identified. As in our previous research¹, an outlier is defined as a score at least five standard deviations above or below the mean.

Data Analysis Software

Negative binomial regression models (to determine the predictors of total trigger pulls, trigger pulls while pointing the gun at the partner/self, and time spent handling a gun) will be run using Stata statistical software version 17 (StataCorp). All other analyses were performed using SPSS version 28 and R statistical software version 4.2.1 (R Project for Statistical Computing).

Data Analyses

Preliminary bivariate and chi-squared tests will be run on the outcome variables. As in our prior studies^{1,2}, two sets of models will be run: (1) a reduced model that includes experimental conditions and gender, and (2) a full model that includes experimental conditions and covariates.

Incidence rate ratios (IRRs) with *SEs*, *z*-tests, and the corresponding 2-tailed *p*-values will be reported for both types of models. Nonsignificant variables (at the 2-tailed .05 significance level) will be excluded from models.

¹ <https://jamanetwork.com/journals/jamanetworkopen/fullarticle/2734799>

² <https://jamanetwork.com/journals/jamapediatrics/fullarticle/2654597>

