The experiment will test the effects of the mere presence of guns in movies on dangerous behavior with guns in children. Participants will be children 8-12 years old. Children will be tested in pairs. Each child will bring a sibling, relative, or friend to the study. Participants and partners will each receive a \$30 gift card (\$5 for watching the safety video at home and \$25 for doing the lab study). The behavioral measure will be whether or not children handle a real (but non-firing) gun and whether they pull the trigger, including at themselves or their partners.

The design will be a 2 (movie clip-guns present vs. movie clip-guns absent) x 2 (gun safety video vs. seatbelt safety video) between-subjects design. Participants will be randomly assigned to conditions, but both children in the dyad will watch the same safety video.

We predict a main effect for type of movie (i.e., children who see movie characters use guns will be more likely to use real guns themselves than will children who do not see movie characters use guns), a main effect for type of safety video (i.e., children who see the gun safety video will be less likely to use real guns themselves than will children who see the car safety video), and an interaction between type of movie and type of safety video (i.e., the movie with guns will have a weaker effect on children who see a gun safety video than on children who see a car safety video).

Procedure

Participants will be told that the study is about what children like to do for fun, such as watch videos and play with toys and games. Participants who agree to participate in the study will be sent consent (adult) and assent (child) forms electronically, along with a pretest for both adult and child to complete, should they consent and assent to participating in the study. These pretests were used in our previous research.^{1,2} After informed consent is obtained, the participants will be sent the safety video for the condition to which they are assigned (i.e., gun vs. car safety video), a short questionnaire about the video, and a \$5 electronic gift card. Approximately one week after being sent the video, the participants will come to the lab for the study.

Experimenters and research assistants will be wearing masks at all times and will be fully vaccinated against COVID-19. The lab space will be sanitized between sessions to ensure participant safety.

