Per OSU policy, all visitors to Ohio State campuses and medical facilities are required to wear masks indoors, regardless of their vaccination status. Children participating in the study and their observing parent or guardian will be required to wear masks for the duration of the experiment in the lab. Outdoor mask wearing is also required on campus for individuals who are unvaccinated when they are unable to maintain socially distancing.

As in our previous study¹, we are using two PG-rated (i.e., "Parental Guidance Suggested. Some Material May Not Be Suitable For Children") Disney films (*National Treasure*, *Rocketeer*) that have been edited to be about 20 minutes. There will be two versions of each film clip, one version with guns left in and one version with guns edited out. Thus, there are four film clips: (1) *National Treasure* with guns, (2) *Rocketeer* with guns, (3) *National Treasure* without guns, and (4) *Rocketeer* without guns.

Participants will be tested in pairs. After viewing the film clip, participants will be placed in a room containing games and toys, with hidden cameras. Participants will be told that

they can play with any of the games and toys in the room for the next 20 minutes. Some games and toys will be scattered about the room, and some will be placed in drawers. Included in the toys are Nerf guns and swords. Two real handguns will be placed in a separate drawer, as in our previous research.^{1, 2} The handguns have been modified so they cannot fire. Inside the magazine, the handgun contains no bullets. Instead, it contains a sensor that counts the number of times the trigger is pulled with sufficient force to discharge the gun. This allows us to distinguish reliably the children who pull the trigger from those who handle the gun but do not pull the trigger. Parents will be asked to predict whether their child will tell an adult if they find the guns, and whether they will handle a gun and pull the trigger. The researcher and the parents will be able to watch the session via a monitor in a control room.

After the 20-minute play period, children will complete a posttest that consists of an attitudes toward guns measure, as in our previous research.^{1, 2}

A thorough debriefing will follow.

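### A gun-history question belongs at baseline, but it is asked in the laboratory, on the natural reading after the trigger-pull test, and could then be reported as a predictor of that test

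*SAP*

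**What the plan says.** The SAP (Data Collection) divides the questionnaire data by place. At home, alongside demographic and trait items, it collects "interest in guns, whether participants had taken a firearm safety course or watched a firearm safety video, and whether participants had a firearm at home". In the laboratory, on iPads, it collects gun attitudes and "whether they have fired a gun before, safety video evaluation, movie evaluation". It does not say where the laboratory items fall relative to the film or the play period.

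The protocol (III.A, Procedure) sends the safety video to the family together with "a short questionnaire about the video, and a \$5 electronic gift card", and then "Approximately one week after being sent the video, the participants will come to the lab for the study". At the visit it goes from the film clip directly to the toy room. Once the 20-minute play period is over, "children will complete a posttest that consists of an attitudes toward guns measure". It describes no other child questionnaire at the visit.

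On analysis, the SAP (Data Analysis Software) says the negative binomial models are meant to find predictors of total trigger pulls, of pulls aimed at self or partner, and of handling time. Under Data Analyses it plans a reduced model with conditions and gender, and a full model with conditions and covariates. The covariates are not listed. IRRs are reported from both models, and variables that are not significant at the two-tailed .05 level are dropped.

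**The concern.** Whether a child has fired a gun is a fact about the child before the trial. It belongs with the other gun-history items, which the SAP collects at home before the visit. Collected after play, it is measured after randomisation, after the safety video and after the outcome. A child who has just pulled the trigger of a real handgun, even a disabled one, may answer yes because of it.

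The possible harm is a result that runs backwards. The models look for predictors of trigger pulls and keep variables by significance. If this item enters the full model, an association created by the outcome itself could be kept and published as evidence that gun experience predicts dangerous behaviour.

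A second, smaller matter is that the two documents place the assessment of the safety video differently, and the protocol's procedure does not mention a laboratory evaluation of it.

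**Working it through.** **Step 1: order of events.** No figure in the plan is at stake here, so the first check is to set the two documents side by side.

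- Home, before the visit: consent and pretests, then the safety video with its questionnaire (protocol, III.A). The SAP's home list has the firearm course or video, firearm at home and interest in guns. It does not have the item on having fired a gun.
- Laboratory: film, play, posttest (protocol, III.A). The SAP's laboratory list has four items. One of them, gun attitudes, is the measure that the protocol puts in the posttest.
- The protocol gives the other three laboratory items no place. Since they are listed with the attitudes measure and only one child questionnaire is described at the visit, the natural reading is that all four come after play.

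**Step 2: how misreporting creates an association.** Let h be the true share with gun history and q the share of trigger-pullers without history who answer yes because of the test. If history has no true effect, h is the same in pullers and non-pullers, and:

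- reported yes among pullers = h + q(1 − h)
- reported yes among non-pullers = h

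Neither h nor q is in the documents. With h = 30% assumed and q = 10%, pullers read 30% + 0.10 × 70% = 37%, against 30% in non-pullers.

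**Step 3: effect on the model's IRRs.** A negative binomial regression was run on 200,000 simulated children, so that the figures show bias and not chance. Every input is an assumption: h = 30%, video IRR 0.5, control mean 2 trigger pulls, gamma shape 0.3 for overdispersion (held at its true value in the fit), about 41% of children pulling the trigger. The model contained the video arm and the reported history.

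| q | Yes among pullers (no true effect) | Item IRR, true value 1.0 | Item IRR, true value 1.5 |
|---|---|---|---|
| 0% | 30.0% | 1.00 | 1.52 |
| 5% | 33.5% | 1.10 | 1.61 |
| 10% | 37.0% | 1.20 | 1.71 |
| 25% | 47.5% | 1.54 | 2.04 |
| 50% | 65.0% | 2.31 | 2.90 |

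The video IRR lay between 0.497 and 0.504 in every row.

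**Step 4: in terms of this trial.** With the planned 208 children and the assumed 41%, 0.41 × 208 ≈ 85 would pull the trigger, and 0.70 × 85 ≈ 60 of them would have no gun history. A q of 5% to 25% is then about 3 to 15 children. The simulation gives the average distortion. It does not give the chance that the item passes the .05 rule with 208 children, which was not calculated.

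**The case against.** A reader might infer something stronger: that the laboratory items come before play, so that evaluating the safety video reminds only the gun-video arm of gun safety just before the test, and the gun-history question breaks the cover story ("Participants will be told that the study is about what children like to do for fun"). The documents do not support this. The protocol goes from film to play with no questionnaire between them, and the SAP lists these items beside a measure that the protocol places after play. The home questionnaires already ask about guns, and the gun-video arm has been sent a gun safety video, so a laboratory question would not be what first reveals the topic. An evaluation made after play cannot change behaviour during play. What remains is only that the SAP does not state the order.

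On the gun-history item, the best defence has three parts.

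- The question is about prior experience and the study guns cannot fire, so many children will answer correctly. This stands: contamination is a risk, not a certainty.
- The SAP does not name the item as a covariate. This also stands, and it makes the harm conditional. But the covariates are not listed at all, so the item is not excluded either.
- The randomised comparison is not threatened. Under the assumptions above this stands too: the video IRR did not move.

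Finally, the protocol's home questionnaire and the SAP's laboratory evaluation of the video may be two separate instruments. The documents do not settle this, so the request is to reconcile them and not to presume that one is wrong.

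**Conclusion.** The point holds and is minor. On the natural reading of the two documents together, a baseline-history item is collected after the outcome it might be used to predict. If it enters the full model, its own IRR and its retention at .05 cannot be taken at face value.

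The size is unknown. With no true effect of history, the illustration gives an IRR of about 1.1 to 1.5 for misreporting by 5% to 25% of trigger-pullers without gun history. This rests on the assumed inputs, on the item being used as a covariate, and on the test affecting answers only through having pulled the trigger. A direct effect of the safety video on how children answer was not examined.

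It would be wrong to conclude that the estimated effect of the gun safety video is biased. Nothing in the documents or in the calculation shows that.

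**What to change.** 1. Move the item on having fired a gun to the home pretest, beside the firearm-course and firearm-at-home items, and word it to cover only the time before this study.
2. For children already run with the item after play, keep that answer out of the covariates and record when it was asked.
3. List the covariates of the full model in the SAP, so that it is clear whether this item is among them.
4. Reconcile the protocol and the SAP on where the safety video is evaluated. If there are two instruments, describe both. State that any laboratory evaluation comes after the 20-minute play period.

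The cost is moving one Qualtrics item and adding a few sentences to the SAP and protocol. The downside is one more gun-related question before the behavioural test, in a home pretest that already has several.

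### The predicted video x movie interaction has no written model term, the SAP's exclusion rule does not protect the randomised factors, pairs sharing a video are not allowed for, and the yes/no measures have no named model

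*SAP*

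**What the plan says.** **Protocol, III.A, Design.** The outcome is framed as yes/no: "The behavioral measure will be whether or not children handle a real (but non-firing) gun and whether they pull the trigger". Three predictions follow: a movie effect, a safety-video effect, and an interaction in which the gun-safety video weakens the movie effect. The design is 2 x 2 between subjects. Children are tested in pairs, and the two children of a pair are given the same safety video.

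**Protocol, III.B and III.D.** The target is 208 children. The only method named is negative binomial regression, justified as suitable for counts.

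**SAP, Data Collection.** Coders record "whether the child found the gun, told an adult about the gun, touched a gun", together with handling time and trigger-pull counts.

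**SAP, Data Analysis Software.** Negative binomial regression is assigned to total trigger pulls, "trigger pulls while pointing the gun at the partner/self, and time spent handling a gun) will be run using Stata statistical software". For everything else only software is given: "All other analyses were performed using SPSS version 28 and R statistical software version 4.2.1".

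**SAP, Data Analyses.** The section opens: "Preliminary bivariate and chi-squared tests will be run on the outcome variables". Two models follow: "a reduced model that includes experimental conditions and gender", and a full one with conditions and covariates. Incidence rate ratios with standard errors and p-values are to be reported for both. The last rule is: "Nonsignificant variables (at the 2-tailed .05 significance level) will be excluded from models". The type of standard error is not stated, and neither document mentions clustering, random effects or generalised estimating equations.

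**The concern.** Three gaps bear on what the trial set out to show.

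1. **Interaction and exclusion rule.** One of the three predictions has no written model term. Even if the analyst adds it, the exclusion rule does not exempt design terms. A predicted effect with p ≥ .05, including a randomised main effect, could disappear from the model instead of being reported with its uncertainty. A term kept only because it passed p < .05 is biased away from zero.
2. **Pairs.** Children in a pair share the safety video and the play session, so their behaviour is likely to be correlated. A test that counts 208 independent children then overstates the information on the video effect, the main question of the trial.
3. **Yes/no measures.** The protocol asks whether a child handles the gun or pulls the trigger. The planned regressions ask how many pulls and how long. No specified model gives an adjusted estimate for the yes/no question with both factors in it.

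**Working it through.** **The plan's own figure.** 2 x 104 = 208 children, as stated. This is a doubling rule; the documents give no event rate, effect size or correlation. All rates and correlations below are therefore assumptions. If all children come in pairs, there are 104 pairs and 208/4 = 52 children per cell.

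**Video effect, pairs ignored.** Both children of a pair have the same video, so the variance of the video contrast is multiplied by 1 + ρ, where ρ is the within-pair correlation. True error of a nominal 5% test = 2 x [1 − Φ(1.96/√(1+ρ))].

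| ρ | 1.96/√(1+ρ) | True error | Effective N = 208/(1+ρ) |
|---|---|---|---|
| 0.2 | 1.789 | 7.4% | 173 |
| 0.4 | 1.657 | 9.8% | 149 |
| 0.6 | 1.550 | 12.1% | 130 |

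Simulation (4,000 trials per setting, 30% or 50% positive, both factors set at pair level) agrees: chi-squared rejects in 7.0–8.3%, 9.6–9.8% and 11.8–12.0%. Unclustered logistic regression rejects in 7.6–12.5%, and pair-clustered logistic in 5.1–5.4%.

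**Interaction, film clip shared within pairs.** Rates are listed as car video without guns / car video with guns / gun video without guns / gun video with guns. Take 30/50/20/25% at ρ = 0.4.

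- Log ratio of odds ratios: [ln(0.50/0.50) − ln(0.30/0.70)] − [ln(0.25/0.75) − ln(0.20/0.80)] = 0.847 − 0.288 = 0.560 (unrounded inputs).
- Variance under independence: (1/0.21 + 1/0.25 + 1/0.16 + 1/0.1875)/52 = 0.391.
- With pairs: 0.391 x 1.4 = 0.548, so SE = 0.740.
- z = 0.560/0.740 = 0.756. Power = Φ(0.756 − 1.96) + Φ(−0.756 − 1.96) = 11.8%; simulated 11.2%.
- 95% interval factor: exp(1.96 x 0.740) = x/÷ 4.3.
- To be kept, the estimate must exceed 1.96 x 0.740 = 1.45 in size, which is 1.45/0.560 = 2.6 times the truth.

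Over ten rate patterns and ρ of 0.2–0.6, simulated power is 7–47%. The rule would then drop a real interaction in 53–93% of trials. When kept, the estimate averages 1.5–4.6 times the true value. At ρ = 0 the highest power is 54% (30/60/25/25%).

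**Interaction, film clip varying within pairs.** The variance factor becomes 1 − ρ. At ρ = 0.2, 0.4 and 0.6, an unclustered interaction test has error 2 x [1 − Φ(1.96/√(1−ρ))] = 2.8%, 1.1% and 0.2%, which is conservative. With an analysis that uses the pairing, power for 30/60/25/25% is 63%, 75% and 90%.

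**Yes/no against counts** (clustered models, ρ = 0.4, 1,000 trials). With 40 v 20% pulling and equal mean pulls, negative binomial power is 54% and logistic power 76%. With 40 v 40% pulling and mean pulls 8 v 3, the count model rejects in 91% and the yes/no model in 4.9%. Neither is better in general: they answer different questions.

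**Handling time (minor).** Negative binomial model-based standard errors depend on the unit. With 50 v 25% handling, mean 180 s and ρ = 0.5, 24% of trials are significant in seconds and 64% in fractional minutes. With pair-clustered standard errors the figure is 60% in both.

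**The case against.** **Experimental conditions may include the product.** In a declared 2 x 2 design with a predicted interaction, that is a fair reading. The exclusion rule may also have been meant for covariates only, and reporting of both models could precede exclusion. This stands as a statement of ambiguity. It does not protect the hypothesis, because the rule as written names no exception.

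**Clustering is unspecified, not ruled out.** True: the standard error type is not given, and the SAP points to earlier studies that cannot be consulted here. But the plan names no clustering, and an ordinary chi-squared test does not allow for pairs.

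**The yes/no measures are not abandoned.** Chi-squared tests are planned and the open-ended software sentence leaves room for logistic regression. This stands: the gap is partial. What is missing is a named model carrying both factors.

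**The interaction figures depend on an unstated design fact.** Only the shared safety video is explicit. Testing in pairs after viewing a clip suggests a shared clip but does not say so. If clips differ within pairs, the result for unclustered interaction tests reverses from liberal to conservative, and power rises. This stands fully. The video-effect inflation does not depend on it.

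**Low interaction power reflects 208 children, and the fix does not add any.** Also true; the fix stops the estimate from being discarded or selectively reported.

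**Conclusion.** The point holds in this form. A stated hypothesis has no written term, the exclusion rule does not protect the randomised factors or their product, within-pair dependence is not addressed, and the yes/no measures have only preliminary unadjusted tests. These textual gaps do not depend on any assumed value.

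The firmest number is the video effect: a nominal 5% test that ignores pairs runs at about 7.4%, 9.8% or 12.1% for assumed correlations of 0.2, 0.4 or 0.6. Interaction power of about 7–47% rests on those correlations, the assumed rates, and a clip shared within pairs; on that footing the rule would often drop a real interaction.

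A reader might infer three stronger things that the documents do not support:

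- That a real interaction will usually be deleted. This needs the shared clip and low power; with clips varying within pairs, or independent children and a large contrast, it can be kept more often than not.
- That logistic models are excluded. They are neither named nor ruled out.
- That the handling-time result turns on the time unit. This arises only with model-based standard errors, and the comparison used fractional minutes, which the plan does not propose.

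**What to change.** 1. Put video, movie and video x movie in every model and keep them whatever their p-values. Limit any exclusion rule to covariates.
2. State whether both children of a pair see the same film clip. Use pair-clustered robust standard errors in all models, with a small-sample correction where available, and replace or supplement the chi-squared tests with a pair-aware test. Clustering alone was slightly liberal for handling time: 5.7–9.2% for negative binomial, against 4.2–6.2% for Poisson with a jackknife standard error and t reference. The jackknife was checked only in that Poisson setting.
3. For handled the gun and for pulled the trigger, fit pair-clustered logistic or modified-Poisson models with the same terms. Report them with confidence intervals alongside the count models.
4. As a minor addition, state the unit for handling time.

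**Cost.** Four extra models on data already coded (two outcomes, reduced and full), one added term in the existing models, a clustering option and one stated unit. There are more results to report. Intervals for the video effect widen by √(1+ρ), about 10%, 18% and 26% at ρ = 0.2, 0.4 and 0.6. The interaction is likely to be imprecise and should be read as an estimate with its interval, not as a decisive test. No new participants or procedures are needed.

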I. Objectives

Our previous research has shown that children exposed to media characters with guns in movies¹ and video games² are more likely to use real guns themselves (e.g., touch them, hold them, pull the trigger). This research tests whether exposure to a gun safety video a week before the study can help counteract dangerous behavior around guns.

II. Background and Rationale

Guns are prominent in movies that target children. An analysis of top selling films found that the depiction of guns in violent scenes in PG-13 films that target youth has increased from the level of G and PG files in 1985 when the rating was introduced, to the level of R films by 2005, to exceed the level of R films since 2012,³ a trend that has continued.⁴ By definition, a PG-13 movie is supposed to have less violence than an R-rated movie. The Motion Picture Association of America says on its website that the violence in a PG-13 movie “does not reach the restricted R category.” Our study shows that it does.

Previous research has shown that when exposed to movie characters that smoke, children are more likely to start smoking themselves⁵; the same is true for characters that drink alcohol⁶. Similarly, research in our lab has shown that children are more to use guns (e.g., handle them, pull the trigger) after exposure to movie characters who use guns.¹ We replicated this study using video games,² and also found that children who had taken a gun safety course were less likely to engage in dangerous behavior around firearms. However, it is difficult to draw causal inferences about the gun safety course because children were not randomly assigned to take or not take a gun safety course.

The present research will aim to reduce dangerous behavior around firearms by first exposing participants to a gun safety video recorded by The Ohio State University Chief of Police. The control video is about car safety. Children will see the videos about a week before they come into the lab. We predict that children will be less likely to engage in dangerous behavior around real firearms if they saw the gun safety video than if they saw the car safety video, even if they see a movie with guns in the lab.

III. Procedures

A. Research Designs, Samples, Measures, and Procedures

Design

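### No primary outcome, effect or model is named and multiplicity is not controlled; if .05 is the threshold for claims, the safety-video question alone carries about an 8–22% false-positive chance

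*SAP*

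**What the plan says.** Protocol I (Objectives) states a single aim: the research "tests whether exposure to a gun safety video a week before the study can help counteract dangerous behavior around guns". Protocol III.A (Design) then makes three directional predictions for the 2 x 2 design. It says "We predict a main effect for type of movie", adds "a main effect for type of safety video", and finally "an interaction between type of movie and type of safety video". The same section describes the behavioural measure in yes/no terms: whether a child handles the gun, and whether the child pulls the trigger.

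The SAP (Data Analysis Software) uses negative binomial models "to determine the predictors of total trigger pulls, trigger pulls while pointing the gun at the partner/self, and time spent handling a gun". Under Data Analyses it says that "two sets of models will be run: (1) a reduced model that includes experimental conditions and gender, and (2) a full model", the latter with covariates. It commits to reporting incidence rate ratios, standard errors, z-tests and two-tailed p-values for both sets. It also plans an unstated number of preliminary bivariate and chi-squared tests on the outcomes. The only significance level in either document is in the last sentence of that section: "Nonsignificant variables (at the 2-tailed .05 significance level) will be excluded from models".

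Nothing in the visible text labels an outcome, an effect or a model as primary, orders the tests, or adjusts for their number.

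**The concern.** The objective is one question, but the plan gives it six model-based answers: the safety-video effect on three outcomes, each in two models. Nothing says in advance which answer counts. If the reduced model is significant for handling time and the other five results are not, the plan gives no basis for deciding whether the video worked. A chance result on any of the six could be read as support. The movie effect and the interaction bring the same problem, and with them the model-based tests number 3 x 3 x 2 = 18.

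At stake is how far a positive report on the video can be taken as confirmatory. The validity of the randomised comparison is not in question.

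**Working it through.** **1. The plan's own figures.** The documents state no overall error rate, power or effect size. The only design figure is the sample size in Protocol III.B, 2 x 104 = 208, which reproduces. It is not linked to any outcome or significance level, so it does not show which test was meant to be primary.

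**2. Inputs from the documents.**
- Outcomes modelled: 3 (SAP, Data Analysis Software).
- Model sets, both reported: 2 (SAP, Data Analyses).
- Predicted effects: 3 (Protocol III.A, Design). The SAP mentions experimental conditions but does not name the interaction as a model term.
- Level: two-sided .05, taken as the threshold for claims. This is an inference, since the SAP attaches it to variable exclusion.

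**3. Inputs assumed.** Correlation between test statistics is 0 to 0.9 across outcomes and 0.8 to 1.0 between the reduced and full models. For different outcomes in different models the two correlations are multiplied. All null hypotheses are true, and each test holds its nominal 5%.

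**4. Reference values if tests were independent**, from 1 − 0.95^k:
- k = 3: 1 − 0.95^3 = 14.3%
- k = 6: 1 − 0.95^6 = 26.5%
- k = 9: 1 − 0.95^9 = 37.0%
- k = 18: 1 − 0.95^18 = 60.3%

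**5. Safety-video effect only: 3 outcomes x 2 models = 6 tests.** Simulation of correlated normal z statistics, giving the chance that at least one has |z| > 1.96:

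| Outcome correlation | Model correlation 0.8 | 0.9 | 0.95 | 1.0 |
|---|---|---|---|---|
| 0 | 21.6% | 19.7% | 18.1% | 14.3% |
| 0.5 | 19.0% | 17.2% | 15.9% | 12.6% |
| 0.8 | 14.9% | 13.5% | 12.5% | 9.8% |
| 0.9 | 12.8% | 11.5% | 10.6% | 8.4% |

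The range is about 8–22%. It is 11–22% where the two models differ (0.8–0.95), and 8–14% if they gave identical results (1.0).

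**6. All three predicted effects: 3 x 3 x 2 = 18 tests**, model correlation 0.8–1.0. The rate depends on how the conditions are coded, which the SAP does not say, so both codings are shown:

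| Outcome correlation | Orthogonal effects | Dummy-coded effects |
|---|---|---|
| 0 | 37–52% | 31–43% |
| 0.5 | 33–47% | 27–39% |
| 0.8 | 27–38% | 21–31% |
| 0.9 | 23–34% | 18–27% |

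The full span is 18–52%, or roughly 20–50%.

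**7. With the fix.** One named outcome, effect and model gives 5% for the primary claim.

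**The case against.** **The .05 level is only the exclusion rule.** This stands as a matter of wording. A reader might infer that the SAP states a rule of testing everything at .05, and it does not. But no other level is given. The exclusion rule is also not limited to covariates, so as written it could decide whether a condition term stays in a model.

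**The tests cannot be independent.** This also stands. A reader might multiply out 18 tests and quote 60%. That figure cannot be reached: both models are fitted to the same children, and trigger pulls aimed at the partner or self are a subset of total pulls. Nor is 27%, the one-model-set rate at outcome correlation 0.8, a floor, since stronger correlation gives 18–23%.

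**The three effects are separate scientific questions.** Whether factorial hypotheses need joint control is debatable. For that reason the conclusion rests on the safety-video figure, which pools no hypotheses. The interaction is also predicted only in the protocol; without it, 3 x 2 x 2 = 12 model-based tests remain, still unranked.

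**The predictions are directional.** A chance result in the wrong direction would not be read as confirmation. Counting only the predicted direction, the same simulation gives about 4–11% for the safety video, but a single test then has 2.5%. The relative inflation is about the same.

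**Both models will be reported.** This limits selection between models, because readers see both sets. It does not say which set decides, and it does nothing about the three outcomes.

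**A primary outcome may be named elsewhere, or the behavioural measure may be it.** A page not included here or the registry record could name one, so the point is limited to the visible text. The protocol's behavioural measure is the nearest candidate. It covers two yes/no behaviours, is not called primary, and is not among the three outcomes that the SAP models.

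**Conclusion.** The point holds for the protocol and SAP as they can be read here: there is no primary test and no multiplicity control. If .05 is the threshold for claims, the chance of at least one false-positive safety-video result is about 8–22% instead of 5%. Over all three predicted effects, counting the interaction, it is roughly 20–50%. Both ranges rest on assumed correlations, true null hypotheses and tests that each hold their nominal 5%. The preliminary bivariate and chi-squared tests and the dropping of nonsignificant variables are not counted and could raise the rates.

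Every two-sided scenario examined exceeds 5%, so the conclusion does not depend on a particular correlation. A reader might go further and infer that any positive result would be spurious, or that the analysts intend to select results. The documents support neither. The gap weakens the confirmatory standing of a claim about the video; it does not invalidate the trial. It should be corrected.

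**What to change.** Before results by condition are seen, add to the SAP one primary test: the safety-video effect in the reduced model (conditions plus gender), two-sided .05, on one outcome. That outcome should be either total trigger pulls or the protocol's yes/no trigger-pull measure. The protocol and SAP must be reconciled on which, and the yes/no measure would need a model for a binary outcome, since the SAP's negative binomial models are for the other three. State that the condition terms stay in the model whatever their p-values.

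Make the movie effect, the interaction (written as a model term) and the remaining outcomes secondary, with Holm-adjusted p-values. Report the full model as a sensitivity analysis.

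One SAP sentence describes other analyses in the past tense. This does not show that results by condition had been seen, but if they had, the choice of primary test should be labelled post hoc.

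The cost is wording only, with no new data. The downside is that secondary effects need smaller p-values. With total trigger pulls as primary, 3 x 3 − 1 = 8 secondary tests remain among the modelled outcomes, and the smallest p-value would have to be at most 0.05/8 = 0.00625.
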